#### Laboratory tests

Routine laboratory tests and assessments will be performed throughout the study, including hematology, blood chemistry, urinalysis, and electrocardiograms (ECGs). Clinically significant changes in laboratory tests or ECGs will be summarized.

Physical examination and vital signs

Physical examinations will be performed to document the baseline condition of the subject and to highlight changes related to AEs. Vital signs will also be assessed, and clinically significant deviations will be reported.

Cortisol-related findings

All subjects will undergo a 250 µg ACTH stimulation test during the Screening period. This test will also be administered at Week 12 (Visit 6), Week 26 (Visit 10), and Week 52 (Visit 14). It may also be performed in the event of clinical symptoms or a low cortisol result.

At all visits (scheduled or unscheduled), specific attention will be given to potential changes related to corticosteroids, as well as symptoms of hypercorticism (see Appendix 6). Should a subject undergo surgery or trauma during the study, particular care should be taken in observing subjects for evidence of inadequate adrenal response.

If hypercorticism or adrenal suppression are suspected, an adequate work-up should be performed to confirm or rule out these findings. Specifically, to monitor for hypothalamic pituitary adrenal (HPA) axis suppression of potential clinical concern, a 250  $\mu$ g ACTH simulation test will also be performed after Screening if any of the following occur:

- During routine laboratory testing completed for the study, the subject has a morning serum cortisol level ≤5 μg/dL (138 nmol/L) (confirmed by 2 blood draws), including at the last on-treatment visit for a subject and, if applicable, Early Termination Visit;
- The subject reports symptoms of hypercorticism;
- The subject discontinues due to HPA axis suppression.

An abnormal result for the ACTH stimulation test is defined as serum cortisol level <16  $\mu$ g/dL (440 nmol/L) at 60 minutes after treatment with 250  $\mu$ g cosyntropin administered intramuscularly. This result is exclusionary if it occurs at Screening/4-week Baseline Symptom Assessment and requires follow-up through recovery of adrenal function if it occurs thereafter. Treatment for HPA axis suppression is discussion in the full protocol. The Sponsor will provide guidelines for safety follow-up and document of restoration of adrenal function in all subjects demonstrating evidence of hypercorticism or HPA axis suppression during the course of the study.

### Electrocardiogram

Electrocardiograms signs will be assessed, and clinically significant deviations will be reported.

Safety endpoints: The safety endpoints of interest are:

- Frequency of TEAEs;
- TEAEs leading to discontinuation;
- Treatment-emergent SAEs;
- Percentage of subjects with serum cortisol level  $\leq 5 \,\mu g/dL$  ( $\leq 138 \,nmol/L$ ) or abnormal ACTH stimulation test (serum cortisol  $< 16 \,\mu g/dL$  [ $\leq 440 \,nmol/L$ ] at 60 minutes);
- The number of subjects discontinuing for HPA axis suppression will be recorded.
- Frequency of oral and esophageal candidiasis.

#### Pharmacokinetic variables:

The following PopPK parameters will be estimated using sparse sampling, as data permit:

- Oral clearance;
- Volume of distribution.

Additional PopPK parameters will be estimated, as appropriate, based on the final structural PK model.

### **Statistical methods:**

Sample size determination: Part 1 will include a sample size with a range of 100 subjects, in which 20 patients are randomized to 1.5 mg HS, 1.5 mg BID, 3 mg HS, 3 mg BID, and placebo (1:1:1:1). Based on these randomization ratios, approximately 80 % of all subjects in Part 1 will be treated with an APT-1011 dosing regimen and approximately 20% of all subjects in Part 1 will be treated with placebo.

### Analysis populations:

- The All Enrolled Population includes all subjects who sign an ICF and are enrolled into the study.
- The Safety Population includes all subjects who receive ≥1 dose of the study drug.

SP-1011-002 APT-1011

- The Intent-to-treat (ITT) Population includes all subjects randomized.
  - A subject who is enrolled in the study and receives study drug, but fails to complete treatment will be considered a dropout.
- The Sparse PK Subgroup includes all subjects who have ≥1 quantifiable PK sample collected for sparse PK evaluations.

Additional analysis populations (e.g., Per Protocol Populations including subjects who complete Part 1, Part 2 Weeks 26 and 52) may be defined in the Statistical Analysis Plan (SAP).

### Statistical methodology:

Subject characteristics

Baseline and demographic information will be summarized using descriptive statistics for continuous and ordinal variables (e.g., age, weight and height [Day 1 only]) and counts and percentages for categorical variables (presence or absence of esophageal strictures, prior response to steroids, sex and race). Body Mass Index (BMI) will be calculated on Day 1.

Primary efficacy analysis for Part 1

Let  $\theta_j$  be the Cochran-Mantel-Haenzel common odds ratio comparing treatment vs. control for histologic response for dose j given randomization strata; with j=1,2,3,4 corresponding to APT-1011 3 mg BID, 1.5 mg BID, 3 mg HS, 1.5 mg HS doses, respectively. There are 4 hypotheses corresponding to the 4 active doses, which will be tested using a gatekeeping strategy to preserve Type I error for each analysis.

1) Primary Hypothesis #1

 $H_0$ :  $\theta_1 \le 1$ 

 $H_1: \theta_1 \leq 1$ 

A stratified Cochran-Mantel-Haenzel test will be used to test primary hypothesis #1, i.e., 3 mg BID vs. placebo, using the randomization strata. If the corresponding one-sided p-value is less than or equal to 0.05, the null hypothesis will be rejected, and subsequently the following hypothesis will be tested:

2) Primary Hypothesis #2

 $H_0: \theta_2 \leq 1$ 

 $H_1: \theta_2 \leq 1$ 

A stratified Cochran-Mantel-Haenzel test will be used to test primary hypothesis #2, i.e., 3 mg HS vs. placebo. If the corresponding one-sided p-value is less than or equal to 0.05, the null hypothesis will be rejected, and subsequently the following hypothesis will be tested:

3) Primary Hypothesis #3

 $H_0: \theta_3 \leq 1$ 

 $H_1: \theta_3 \leq 1$ 

A stratified Cochran-Mantel-Haenzel test will be used to test primary hypothesis #3, i.e., 1.5 mg BID vs. placebo. If the corresponding one-sided p-value is less than or equal to 0.05, the null hypothesis will be rejected, and subsequently the following hypothesis will be tested:

4) Primary Hypothesis #4

 $H_0$ :  $\theta_4 \le 1$ 

 $H_1: \theta_4 \leq 1$ 

A stratified Cochran-Mantel-Haenzel test will be used to test primary hypothesis #4, i.e., 1.5 mg HS vs. placebo. If the corresponding one-sided p-value is less than or equal to 0.05, the null hypothesis will be rejected.

Note the gatekeeping strategy only allows formal hypothesis testing of 1.5 mg HS or 1.5 mg BID if the higher doses meet statistical significance. Given prior studies with histologic endpoints, there is a strong rationale suggesting that higher doses will have a greater benefit on the primary efficacy endpoint of

Adare Pharmaceuticals SP-1011-002

APT-1011

histology.

Efficacy analysis for Part 2

Sustained EoE response will be assessed in subjects who complete both Part 1 and Part 2 and complete Week-26 and 52 evaluations. This will be assessed by the primary endpoint.

Other measures of efficacy will be assessed at Week 26.

Efficacy will be summarized for histologic non-responders from Part 1 who are treated in Part 2.

Other measures of efficacy will be assessed at Week 52.

The primary focus of Part 2 will be descriptive in nature.

Secondary and exploratory efficacy analysis

Formal statistical hypothesis testing will be used to evaluate treatment benefit with respect to the reduction in number of dysphagia episodes. For each dose that meets the criterion for statistical significance on the primary efficacy outcome, a Wilcoxon Rank-Sum test will be used to test whether the reduction in the number of dysphagia episodes from baseline is larger for the treatment group compared to the control. The hypothesis to be tested is:

 $H_0: R_{1i}(x) \le R_{0i}(x)$ 

 $H_1: R_{1i}(x) > R_{0i}(x)$ 

Where  $R_{ij}(x)$  is the distribution function for the reduction in number of dysphagia episodes for treatment group i (=0 for control, 1 for treatment) and dose j. Holm's step-down procedure will be used to control the overall Type I error at 0.05, where the number of doses considered for inferential testing is equal to the number of doses that meet statistical significance for the primary efficacy analysis.

Statistical tests to compare each APT-1011 dosing group with placebo will be performed for other secondary efficacy endpoints, but the corresponding p-values will be considered as descriptive rather than inferential. The secondary endpoints will be analyzed via a stratified Cochran-Mantel-Haenzel test for categorical endpoints and analysis of covariance or Wilcoxon Rank-Sum tests for change from baseline endpoints, except for the endpoint of time to relapse after initiation of double-blind treatment in Part 2, which will be analyzed using Kaplan-Meier methods.

As a secondary efficacy analysis, all 4 doses of active treatment will be pooled and compared to placebo with a stratified Cochran-Mantel-Haenzel test. Additionally, Bayesian hierarchical modeling will be used for both the primary efficacy endpoint and reduction in number of dysphagia episodes, in which dose-response modeling is used to estimate the difference between each active dose and placebo. Additionally, a logistic regression model using both dose and frequency and dose-frequency interaction will be used to analyze the primary endpoint. Subgroup analyses and regression models will also be conducted on primary and key secondary endpoints to assess regional effects and relationships with demographics (age, gender, race, ethnicity, PPI status, and strata variables).

Safety analyses

The incidence of TEAEs will be summarized by system organ class (SOC) and preferred term. Separate summaries by maximum severity (all AEs) and relationship to study drug (SAEs only) will be provided. The incidence of TEAEs leading to discontinuation from the study and treatment-emergent SAEs will also be summarized. In subjects who change dosing groups, the TEAEs will be attributed to actual dose at the time of the event.

Clinically significant changes of potential clinical interest in clinical tests will be summarized including hematology, chemistry, urinalysis, ECG, cortisol, vital signs, and bone mineral density. No statistical testing of safety endpoints will be performed. Shift tables may be produced, if needed. The number of subjects discontinuing due to HPA axis suppression or positive ACTH stimulation tests will be summarized.

Population pharmacokinetics

A PopPK analysis will be performed based on sparse plasma concentration data. It will be performed using the nonlinear mixed-effects software, NONMEM, Version 7.2.0 or later or other appropriate nonlinear mixed-effects modeling software. The structural PK model will include oral clearance and volume of

distribution as fixed-effect parameters. Additionally, the intersubject variability in the parameter estimates and the random residual error in the data will be estimated with appropriate error models. The optimal base model will be selected according to the standard criteria such as minimum objective function value and diagnostic plots. Evaluation of renal and hepatic functions and concomitant medications will be included in the PopPK model. A separate PopPK report will be generated as an appendix to the clinical study report.

Exploratory PK/PD analysis

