### Study design:

Study design: This is a randomized, double-blind, placebo-controlled dose-ranging study of 4 total daily doses of APT-1011 versus placebo in 100 adult subjects (≥18 years of age) diagnosed with EoE.

During the single-blind run-in/baseline symptom assessment, the subjects will receive placebo 30 minutes after breakfast and hora somni (HS; at bedtime). Four doses of study drug will be administered: Placebo 30 minutes after breakfast and 1.5 mg HS APT-1011, 1.5 mg twice daily (BID) (30 minutes after breakfast and at bedtime; total daily dose of 3 mg) APT-1011, Placebo 30 minutes after breakfast and 3 mg HS (at bedtime), and 3 mg BID (30 minutes after breakfast and at bedtime; total daily dose of 6 mg) APT-1011, and matching placebo administered 30 minutes after breakfast and HS (at bedtime).

The 100 subjects will be randomized in a 1:1:1:1:1 to receive placebo or one of the active doses into Part 1 of the study. As described below, the treatment that a subject receives in Part 2 depends on their histologic response status at Week 12.

Randomization will occur in a double-blind manner using an integrated Interactive Web Response System (IWRS), and will be stratified by the presence or absence of a history of or current esophageal stricture and history of a prior positive steroid response to any corticosteroid treatment previously received to treat the subject's EoE captured with demography.

Efficacy (including sustained EoE response and patient-reported outcomes [PRO]), safety, and PK of APT-1011 will be examined.

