## 8.1.1 Expected Number of Subjects by Part

The following assumptions were used:

- The 1:1:1:1 (1.5 mg HS: 1.5 mg BID: 3 mg HS, 3 mg BID: placebo) randomization ratios will remain constant throughout the study.
- Based on these randomization ratios, approximately 80% of all subjects in Part 1 will be treated with an APT-1011 dosing regimen and approximately 20% of all subjects in Part 1 will be treated with placebo.
- Based upon the PR-021 study, which had slightly different histologic response criteria, it is expected that approximately 60% of patients on active treatment are expected to be a histologic responder compared to 10% on placebo. The lowest dose may be less effective.
  - Assuming a 60% histologic response rate for the 3 highest active doses of 1.5 mg BID, 3 mg HS, 3 mg BID, a 20% response rate for 1.5 mg HS, and a 10% response rate for placebo, it is expected that overall approximately 50% of active treatment will be responders at Week 12 (40 out of 80).
  - o It is expected that at Week 26 an additional 20% will drop out who were previously responders and of the PART 1 non-responders that 40% will still be non-responders.
  - After Week 26, of the remaining subjects, it is expected that approximately 20% will dropout before Week 52.

Given these assumptions, it is expected that approximately 42 patients will be responders and complete Week 26, and about 34 of those responders will complete Week 52.

The power for testing each active dose versus placebo given a histologic response rate of 60% active treatment and 10% placebo for the primary endpoint (Part 1) is equal to 97.5% (one-sided Type I error = 0.05). Additionally, the power for achieving statistical significance for all 3 of the highest active doses of 1.5 mg BID, 3 mg HS, 3 mg BID via the gatekeeping hypothesis testing approach assuming independence is approximately 0.93.

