16.1.5. SECONDARY ANALYSES OF THE PRIMARY EFFICACY VARIABLE

- Bayesian hierarchical modeling will be used for both the primary efficacy endpoint and reduction in number of dysphagia episodes, in which dose-response modeling is used to estimate the difference between each APT-1011 dosing group and placebo.
- Terms in the Bayesian models will include dose (3 mg, 1.5 mg, or 0 mg), frequency (BID or HS, with placebo subjects included as BID), and the two randomization strata. Posterior estimates for each of the model coefficients will be generated through Monte Carlo Markov Chains (MCMC) using the Metropolis random walk sampling algorithm. Initially the first 2000 simulations will be discarded for burn-in and the subsequent 10000 samples retained for posterior estimation. Trace iteration plots and autocorrelation plots of the simulated samples will be examined with standard diagnostic tests to establish convergence of the posterior samples. If sufficient convergence of all parameters has not been achieved the burn-in period and number of simulations will be revised and different sampling algorithms will be considered.
- The proportion of responders at each dose level and frequency will be estimated from the respective posterior distributions. Estimates of the difference in the proportion of responders between each active dose level and placebo will be calculated using the distributions of the differences between posterior estimates along with 90% credible intervals of these estimates. The probability that the difference is greater than 0 will also be displayed. In addition the posterior distributions of each difference estimate will be produced along with the estimated dose-response curve. Estimates of the dosing frequency and stratification effects will also be displayed for all dose groups.
- A logistic regression model using both dose and frequency and dose-frequency interaction will be used to analyze the primary efficacy variable. Separate terms will be included in the model for dose (3 mg, 1.5 mg or 0 mg (placebo) frequency (BID or HS, with placebo subjects included as BID) and dose-frequency interaction.

Two models will be used. One containing just dose, frequency and dose-frequency interaction. The other will

Author:

Version Number: 3.0

Version Date: 06NOV2019

Template No.: CS TP BS016 Revision 5

Reference: CS WI BS005

Effective Date: 01Apr2018

Page 36 of 70

additionally contain randomization strata.

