- Odds ratios will be provided per 1.5 mg increase in dose and per 1 unit increase in daily dose frequency. 3 mg doses will be coded as 2, 1.5 mg doses will be coded as 1, and placebo will be coded as 0. For frequency, BID will be coded as 2, and HS will be coded as 1. The variables will be analyzed in continuous form, but re-coding in this way will allow for provision of the odds ratios per 1.5 mg increase.
- o If the dose-frequency interaction term is significant at the 10% level, separate logistic regression analyses models will be fitted for each dose level separately, with dose frequency in the model (and repeated with the randomization strata also in the model). If the interaction term is not significant, a model without the interaction terms will be used to estimate the effects of dose and frequency
- The primary efficacy variable will be summarized for each subgroup defined in section 7.5, by each of the five randomized dosing groups.
 - For the dose with maximum utility (i.e. largest effect size), logistic regression will be used to estimate Odds ratio of APT-1011 vs Placebo within each subgroup
 - For other doses, no statistical testing will be performed for results within each subgroup.

All these secondary analyses of the primary efficacy variable will be performed on the FAS analysis set.

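### The SAP's dose-frequency model takes dose as the amount per administration, so its frequency odds ratio measures a doubled daily dose and not once- versus twice-daily dosing at equal daily dose

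*Protocol*

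**What the plan says.** The protocol (Synopsis, Statistical methodology, and Section 8.8.3) names the model only: "a logistic regression model using both dose and frequency and dose-frequency interaction will be used to analyze the primary endpoint". It does not define dose.

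SAP 16.1.5 does: "Separate terms will be included in the model for dose (3 mg, 1.5 mg or 0 mg (placebo) frequency (BID or HS". Placebo is placed with the twice-daily arms: "frequency (BID or HS, with placebo subjects included as BID) and dose-frequency interaction". The scores are numeric and treated as continuous: "3 mg doses will be coded as 2, 1.5 mg doses will be coded as 1, and placebo will be coded as 0", with BID = 2 and HS = 1. The reported effects are stated as "Odds ratios will be provided per 1.5 mg increase in dose and per 1 unit increase in daily dose frequency". If the interaction is not significant at 10%, it is dropped and the main-effects model estimates dose and frequency. If it is significant, frequency is fitted separately at each dose level. A second version adds the randomization strata. The Bayesian model in the same section uses the same dose and frequency terms and also displays a frequency effect.

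The protocol (Synopsis, Study design, and Section 4.1) and SAP 3.1 describe the trial as a "dose-ranging study of 4 total daily doses of APT-1011 versus placebo". The regimens in SAP 3.1 and protocol Table 5-1 give three totals: 1.5 mg/day (1.5 mg HS), 3 mg/day (1.5 mg BID and 3 mg HS) and 6 mg/day (3 mg BID).

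**The concern.** The HS arms take placebo in the morning. At a fixed value of the model's dose term, moving from HS to BID therefore takes the daily dose from 1.5 to 3 mg, or from 3 to 6 mg. No term holds daily dose constant, so the frequency odds ratio mixes regimen with the amount of drug. The one pair of arms that separates them, 3 mg HS and 1.5 mg BID, is not contrasted directly anywhere in SAP 16.1.

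Defining the dose-response and selecting a Phase 3 dose are secondary objectives, and protocol Section 2.5 gives once-daily convenience as one reason for the dose taken forward. A table row headed frequency invites the reader to take it as the answer on once- versus twice-daily dosing, and the SAP gives no caveat.

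**Working it through.** **Inputs.** Response rates from protocol 8.1.1: "Assuming a 60% histologic response rate for the 3 highest active doses of 1.5 mg BID, 3 mg HS, 3 mg BID", with 20% for 1.5 mg HS and 10% for placebo. There are 20 subjects per arm (Section 8.1). Tests are one-sided at 5% with 90% intervals (SAP 6.6). Coding is from SAP 16.1.5.

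**Check that the inputs are read correctly.** The documents give no figure for this model, so I reproduced the stated power for 60% versus 10%. With pooled rate 0.35, z = [0.5 × √20 − 1.645 × √(2 × 0.35 × 0.65)] / √(0.24 + 0.09) = (2.236 − 1.110) / 0.574 = 1.96, which gives 97.5%. Its cube is 0.927. Both match Section 8.1.1 (97.5% and about 0.93).

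**Data and coding.** Expected counts:

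| Arm | Responders | Dose code | Frequency code | mg/day |
|---|---|---|---|---|
| 3 mg BID | 12/20 | 2 | 2 | 6 |
| 1.5 mg BID | 12/20 | 1 | 2 | 3 |
| 3 mg HS | 12/20 | 2 | 1 | 3 |
| 1.5 mg HS | 4/20 | 1 | 1 | 1.5 |
| Placebo | 2/20 | 0 | 2 | 0 |

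The two 3 mg/day arms both respond at 60%, so the equal-dose regimen odds ratio built into these rates is 1.0.

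**Step 1, interaction model.** The interaction coefficient is −0.667 (SE 0.812), two-sided p = 0.41. On expected counts the SAP rule leads to the main-effects model.

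**Step 2, main-effects model.** logit(p) = −3.107 + 1.276 × dose + 0.746 × frequency.
- Frequency odds ratio: exp(0.746) = 2.11. With SE 0.473, the 90% CI is exp(0.746 ± 1.645 × 0.473) = 0.97 to 4.59; z = 1.575, one-sided p about 0.058.
- Dose odds ratio per 1.5 mg: exp(1.276) = 3.58.
- Implied 1.5 mg BID versus 3 mg HS: exp(0.746 − 1.276) = 0.59 (90% CI 0.27 to 1.30).

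**Step 3, role of placebo.** With the four active arms only, the frequency and dose odds ratios are both 2.33. Their ratio is 1.00, so the 0.59 comes from fitting placebo on the same linear scale. The frequency odds ratio well above 1 does not depend on placebo. Coding placebo as HS gives 2.48.

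**Step 4, models by dose level, if the interaction is significant.** At 1.5 mg, BID versus HS is (0.6/0.4)/(0.2/0.8) = 6.0. At 3 mg it is 1.0. Each still doubles the daily dose.

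**Step 5, equal-dose estimate.** Directly, 1.5 mg BID versus 3 mg HS at 12/20 each has odds ratio 1.00 and SE of the log √(1/12 + 1/8 + 1/12 + 1/8) = 0.645, so the 90% CI is 0.35 to 2.89. The risk difference is 0 ± 1.645 × √(2 × 0.6 × 0.4/20), about ±25 percentage points. Modelling daily dose linearly instead gives a regimen odds ratio of 0.78 (five arms, placebo coded BID) or 1.38 (active arms only). The direct contrast avoids that dependence on functional form.

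**Sampling variation.** In 2,000 simulated trials at the planning rates, the interaction reached 10% in about 18%. The median main-effects frequency odds ratio was 2.13, and it favoured BID at one-sided 0.05 in 47%.

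**The case against.** The strongest reply is that strength by frequency is the trial's actual two-by-two layout of active arms and that the SAP defines both terms openly. Adding a second 1.5 mg tablet, 20% to 60% at the planning rates, is then a real effect and not an artefact. The drug is expected to act topically, so total daily dose need not be the only meaningful scale. This stands. The odds ratio is a valid description of a second tablet, and the documents nowhere claim that it is an equal-dose comparison. The defect is in what the label invites and in the missing contrast.

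A reader might go further and infer that the analysis argues wrongly against once-daily dosing, or led to a wrong dose choice. The documents do not support that. The five-arm fit, read whole, implies 0.59 for 1.5 mg BID versus 3 mg HS, which leans towards the once-daily arm. Protocol Section 2.5 reports that 3 mg HS had already been chosen after the Week 12 analysis. SAP 7.4 treats this testing as descriptive.

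Nor is the 2.11 a significant BID advantage: its expected interval includes 1. Following the SAP's steps raises the simulated share favouring BID to about 58%, against about 4% for the direct equal-dose test. However, that count uses only the 1.5 mg models when the interaction is significant, where the 3 mg models have an expected odds ratio of 1.0. Under other patterns in which response depends only on daily dose (30/50/50/70% and 40/55/55/70%), the share falls to 39% and 20%.

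It is also fair that the arms are each compared with placebo and that the Bayesian analysis estimates response at each dose level and frequency. A reader can therefore set the two 3 mg/day arms side by side. What is absent is the contrast with its interval.

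**Conclusion.** The point holds as a matter of interpretation and reporting. The frequency odds ratio in SAP 16.1.5 estimates a second tablet of the same strength. At the planning rates it is expected to be 2.11 (90% CI 0.97 to 4.59; 2.33 in active arms only), and the five-arm fit implies 0.59 at equal daily dose. Neither recovers the value of 1.0 in those rates.

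The size rests on the Section 8.1.1 rates, chiefly the assumed step from 20% to 60% at 1.5 mg, and equality of regimens can be checked only at 3 mg/day. The version with randomization strata could not be evaluated because no stratum rates are given. The primary test and its type I error are unaffected, and no wrong dose decision is demonstrated.

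**What to change.** In SAP 16.1.5:
- Report 3 mg HS versus 1.5 mg BID directly, as a risk difference and an odds ratio with 90% CIs, as the estimate of regimen at equal daily dose. SAP 4.2 makes the Week 12 analysis final for Week 12 endpoints and protocol Section 2.5 already reports its result, so mark the contrast post hoc if it is added after that unblinding.
- Label the existing frequency odds ratio as a second tablet of the same strength (doubles the daily dose), and put the same note on the Bayesian frequency effect.

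In the protocol Synopsis, Sections 2.5 and 4.1, and SAP 3.1, describe the design as four regimens at three total daily doses.

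The cost is wording and one contrast on existing data. The drawback is precision: the contrast rests on 40 subjects, with an odds ratio interval of about 0.35 to 2.89 at 60% response. It can describe the regimen question but not settle it.
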